### c. Background

- i. Physical activity (PA) is associated with many personal and societal benefits, e.g., alleviation of pain and improvement in physical function (1). Despite benefits, only 16% of people age 65+ engage in recommended levels of PA. Pain has been cited as a reason for PA intervention dropout (2,3). Research is needed to identify mechanisms that can sustain participation in behavioral interventions when barriers such as pain are present. One promising mechanism is interpersonal and social resources. Social ties affect health behaviors and have powerful effects among lower income older adults and those with health problems.
  1. Centers for Disease Control and Prevention Physical Activity – About Physical Activity – Why it Matters. Last accessed January 14, 2019 from <https://www.cdc.gov/physicalactivity/about-physical-activity/why-it-matters.html>.

2. Centers for Disease Control and Prevention Adult participation in aerobic and muscle-strengthening physical activities - United States, 2011. *Morb Mortal Wkly Rep.* 2011;62:326-330. MMWR. [PMC free article] [PubMed] [Google Scholar]
3. Centers for Disease Control and Prevention Physical Activity: How Much Physical Activity Do Older Adults Need? Last accessed January 14, 2019 from [http://www.cdc.gov/physicalactivity/basics/older\\_adults/](http://www.cdc.gov/physicalactivity/basics/older_adults/).

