- y. Participants will be asked to complete a 40-minute post-program (follow up) interview over the phone, administered through Qualtrics. They will again be asked questions about things they do, physical activities they engage in, their social relationships with other residents in the community, and their health. They will also be asked questions intended to measure the usefulness and satisfaction with the program. In the post-program interview we will ask participants again whether they know each of the other participants in their cohort, and for each they do know, how much they respect them. The purpose of asking these questions in the post-program interview is to determine if the social connections between participants change over the course of the intervention. This is required in order to determine if and how the Advisory Committee members' position in the network of participants (in terms of being the most respected) changes. It is hypothesized that there will be an increase in the number of participants reported known and also the level of respect will increase. If supported, this will provide evidence of an important secondary outcome of the intervention, which could be useful in sustaining participants' engagement of behaviors introduced during the intervention.

- z. Finally, following the post-program interviews, participants will again be asked to wear an ActivPAL physical activity monitoring device on their thigh for 7 consecutive days. The study team will then visit the participants to pick-up the ActivPAL device and all other study materials (e.g., the tablet). At this visit, the participants will receive the remaining incentive in cash and told that this concludes their participation in the study.
    - aa. Participants will receive \$10 for completing the study screening assessment and if they are eligible to participate, they will receive an additional \$25 for completing baseline and \$30 for completing the follow-up study assessments. Additionally, they will receive \$20 to wear an activity monitor for seven consecutive days at baseline and follow-up (\$10 for wearing it at baseline and \$10 for wearing it at follow-up), for a total of \$85 for participating in all parts of the study. Agents of change (AoC) will receive \$100 as a token of appreciation for their time to serve in this role, which will be provided following the committee's third (and last) meeting.

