    - bb. Participation will be ended prematurely if a study participant contacts the study team and indicates that they would like to withdraw from the study or if the Occupational Therapist administering the intervention determines at any point that it is not safe for the participant to continue participating. If a participant withdraws from the study, the individual's data will be retained unless the participant requests to have their data destroyed. A participant's data will be destroyed upon their request. However, once findings are used in an analysis it will not be possible to remove a participant's information.
    - cc. Deidentified data gathered during screening interviews (including from people who are found to be ineligible) will be kept to meet reporting requirements of the study sponsor (the National Institutes of Health). Identifying information including name, address, and phone number of those ineligible will only be kept to mail the screening interview incentive and will then be destroyed/deleted following the mailing. Identifying information of those eligible will be kept for study communication purposes. For participants who did not agree to be contacted for participation in future research, their identifying information will be destroyed/deleted at the time of study conclusion (i.e., after last visit is made to collect study materials and provide the last incentive). For participants who did agree to be contacted again in the future, their identifying information will be retained.

Advantages of providing participants with tablets and using a virtual format for the OT intervention include improving accessibility by providing an opportunity for participants to engage in the program activities from the convenience of their home/apartment unit. This methodology and mode of delivery of the intervention aims to address potential barriers to sustain participation.

Timeline per cohort:

Week 1-2:

Recruitment, eligibility screening, pre-intervention interview, and accelerometry data collection, Social network analysis and Identification of agents of change (AoC)

Week 3:

Formation of Advisory Committee, pre-intervention OT remote 1-on-1 meetings

Week 4-7:

OT-led remote group sessions, brief weekly remote 1-on-1 check-ins

Week 8:

Post-intervention OT remote 1-on-1 meetings

Week 8-9:

Post-intervention interviews and accelerometry data collection

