- c. AIM 2) Evaluate feasibility of intervention implementation. Process outcomes will be examined following intervention implementation to determine which components were feasible. The process evaluation will be guided by a framework for evaluating complex interventions that assesses implementation, mechanisms of impact, and context. Process measures will include: 1) number of original AoC who accept invitation to serve on the Advisory Committee; 2) number of committee meetings attended by AoC; 3) number of individual (one-on-one) activities attended by study participants; 4) number of group activities attended by study participants; 5) total number of intervention activities attended by study participants; and 6) number of remote activities that study participants attended via zoom. Hypotheses: The following process hypotheses will be tested H2a: At least 75% (3 of 4) of identified AoCs will accept the invitation to serve on Advisory Committee; H2b: AoC will attend at least 2 of 3 committee meetings; H2c: Participants will on average participate in at least 70% (7 of 10) of intervention activities.
  - i. Data analysis plan:
    1. Quantitative analysis: Descriptive analysis of process outcomes and intervention usefulness/satisfaction data from post-intervention interviews will be conducted using statistical software (e.g. SPSS). This will include examination of variable frequencies, measures of central tendency, and sample variation.
    2. Qualitative analysis: Analysis of open-ended data from questions about the usefulness and satisfaction with specific intervention

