## VI. Informed consent

- a. We will obtain informed consent three times during the study for three different types of participation: 1) participation in a screening interview to determine if the participant is eligible to participate; 2) participation in the intervention program and evaluation aspects (i.e., pre and post-program interview and wearing of an activity monitor (activPAL) for 7-days after the pre and post-program interviews; and 3) for two specific participants (i.e., the most respected in the cohort) agreement to serve on the program Advisory Committee.
- b. First, informed consent will be obtained prior to participation in the screening interview. Screening interviews will be conducted in-person at the housing community and also by telephone. If the screening interview is conducted by phone, we will obtain verbal consent. The date that verbal consent is provided to participate will be noted on a copy of the informed consent document by the interviewer along with the participant's name. Following the screening interview, the dated copy will be stored with the study records and a blank copy will be mailed to the participant to keep for their records. If the screening interview is conducted in-person, prior to beginning the interview the interviewer will go over the informed consent document with the participant. The participant will then be asked to sign the form if they consent to participate in the screening interview. The signed copy will be kept and stored with the study records, and the participant will be given an unsigned copy for their records.
- c. If a participant is screened over the phone and they are determined to be ineligible to participate in the study, following their screening interview, they will be mailed a copy of the screening consent.
- d. If a participant is determined to be eligible to participate in the study, following their screening interview two appointments will be set-up: 1) to visit the participant in-person in the housing community to obtain signed consent to participate in the study and drop-off study materials. This consent will be for participation in the pre-program/intervention interview, pre-intervention accelerometry data collection, the

intervention itself, the post-intervention interview, and post-intervention accelerometry data collection. 2) to complete the first study activity, a pre-intervention interview over the telephone.

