  - iii. Participant data will be deleted from the device before the device is used again with another study participant.
  - iv. There is a serial number located on the device, which will be linked to a participant's unique study ID, which will be stored in the aforementioned password-protected file at the University of Michigan.
  - v. If the device is lost or stolen, it will not be possible for the data stored on the device to be linked back to a specific study participant. Protection of confidentiality will be ensured during required data and safety monitoring and reporting. Specifically, data will be presented in a blinded manner in the quarterly data and safety reports submitted to the study's locally appointed safety officer, and the study sponsors.

\*\*\*\*\*Ame00137652\*\*\*\*\* Protection of confidentiality will be ensured during required data and safety monitoring and reporting. Specifically, data will be presented in a blinded manner in the data and safety reports submitted to the study's sponsor.

IX. Subject payments or incentives

- a. Participants will receive \$10 for completing the study screening assessment and if they are eligible to participate, they will receive an additional \$25 for completing baseline and \$30 for completing the follow-up study assessments. Additionally, they will receive \$20 to wear an activity monitor for seven consecutive days at baseline and follow-up (\$10 for wearing it at baseline and \$10 for wearing it at follow-up), for a total of \$85 for participating in all parts of the study. Agents of change (AoC) will receive \$100 as a token of appreciation for their time to serve in this role, which will be provided following the committee's third (and last) meeting.
- b. The incentives are a token of appreciation of the time taken to complete data collection activities. Amounts are consistent with others similar in time. For agents of change (AoC), their incentive is a token of appreciation for the time to participate in multiple meetings as well as involvement in intervention administration (e.g., reminding others to attend meetings).
- c. Participants will only be compensated accordingly for completing the specific study activity. If they withdraw from the study, they will be compensated for the activities they completed prior to withdrawal.

X. Healthcare Treatments and Procedures

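### An OT safety stop appears to end follow-up as well as the intervention, so satisfaction and pre-post change would omit the residents who were stopped

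*Combined protocol and SAP*

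**What the plan says.** Section II.bb gives two routes to early ending. The first is the participant's: "Participation will be ended prematurely if a study participant contacts the study team and indicates that they would like to withdraw from the study". The second is the therapist's: ending follows if "the Occupational Therapist administering the intervention determines at any point that it is not safe for the participant to continue participating". Both have the same consequence, the premature end of participation. For those who withdraw, the section adds that "the individual's data will be retained unless the participant requests to have their data destroyed". It says nothing about collecting further data after either route.

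Section VI.a shows what participation covers. The second of the three consents is for "participation in the intervention program and evaluation aspects (i.e., pre and post-program interview and wearing of an activity monitor", so intervention and assessments are agreed to together. Section II.z tells participants that their participation is over only at the last visit, after the second activPAL week. Section IX.c adds: "If they withdraw from the study, they will be compensated for the activities they completed prior to withdrawal".

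The outcomes at issue come from the end of the study. Of the post-program interview, section II.y says: "They will also be asked questions intended to measure the usefulness and satisfaction with the program". Section III.c (Aim 2) then plans: "Descriptive analysis of process outcomes and intervention usefulness/satisfaction data from post-intervention interviews will be conducted". The open-ended answers used for the qualitative themes come from the same interview. Sections III.d and III.e build change scores in self-reported function, activity and pain, and in activPAL time, from pre- and post-program values. Section III has no missing-data rule, no definition of who is analysed for each outcome, and no comparison of those with and without follow-up.

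**The concern.** A resident whom the OT stops partway through has not withdrawn consent. If the stop also ends data collection, the study loses that person's view of the program and their post-program function, activity and pain, although they may be willing to give them.

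The loss is unlikely to be random. The Background (I.c) notes that "Pain has been cited as a reason for PA intervention dropout" and asks what can sustain participation when such barriers are present. Pain is also a measured outcome under Aim 3. Residents for whom continuing was judged unsafe are informative about which components were feasible, which is the question of Aim 2. If they are missing, satisfaction and change would tend to look better than they were across everyone enrolled, and the themes would lack their accounts.

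**Working it through.** **Step 1. Does an OT stop end follow-up?** Three places have to be read together.
- II.bb: an OT safety decision ends participation.
- VI.a: participation, as consented to, includes the post-program interview and activPAL wear.
- II.z: participation normally concludes after the second wear week.

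Ending participation prematurely therefore most naturally means ending it before those assessments. No section provides for them afterwards. This is an inference from the text; the plan does not state it outright.

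**Step 2. Which outcomes need post-program data?**
- Needed: usefulness and satisfaction, open-ended themes, self-report change scores, activPAL change scores.
- Not needed: AoC acceptance and committee attendance (H2a, H2b), activities attended (H2c), and participation by AoC tie and by baseline pain (H3a, H3b). These use counts recorded during the program and baseline data.

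**Step 3. The plan's own figures.** Sample size: 2 cohorts × 12 = 24, as stated in III.a. Activities: 1 initial meeting + 4 group sessions + 4 check-ins + 1 final meeting = 10, and 7/10 = 70%, as stated in H2c. Both reproduce. No dropout rate or dropout allowance is given.

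**Step 4. Illustration of size.** Let k be the number of the 24 without post-program data. The values of k are assumptions.
- Participants with change scores: n = 24 − k.
- 95% CI half-width for a mean change, in SD units: t(0.975, n − 1)/√n.
- Shift in the mean if the lost participants' change differs from the others' by D SD: the mean over all 24 differs from the observed mean by (k/24) × D. D = 1 is assumed.
- For any yes/no satisfaction item, the share among all 24 is known only to within a range k/24 wide, because each missing answer could go either way.

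| k | n | CI half-width (SD) | Shift, D = 1 (SD) | Range width, k/24 |
|---|---|---|---|---|
| 0 | 24 | 0.42 | 0 | 0% |
| 2 | 22 | 0.44 | 2/24 = 0.08 | 8.3% |
| 4 | 20 | 0.47 | 4/24 = 0.17 | 16.7% |
| 6 | 18 | 0.50 | 6/24 = 0.25 | 25.0% |

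The loss of precision is small. The possible shift and the wider range for satisfaction matter more, and the planned analyses would show neither.

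**The case against.** The strongest reply is that the text is narrower than it looks, and much of that reply stands.

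- A reader might infer that anyone who stops attending, for instance because of pain, drops out of the data, leaving completers only. The documents do not support this. The participant's route in II.bb is a request to leave the study, and II.y and II.z ask for the post-program interview and activPAL wear with no attendance condition. A resident who stops coming but does not withdraw is still due for both.
- A reader might infer that the whole feasibility evaluation excludes those who stop early. It does not. The six Aim 2 process measures are counts of acceptance and attendance, and withdrawn participants' data are kept unless they ask for destruction. Low attendance among residents with more pain would be visible under H3b.
- The Background says only that pain has been cited as a reason for dropout. It does not say that pain caused it or will cause it here.
- The OT asks about injury and discomfort at the weekly check-ins (IV.d.i), so safety-related reasons would be heard. They are not among the Aim 2 process measures, however, and no reason for stopping is planned as data.
- II.bb could be read as ending only the intervention, since a telephone interview is hardly unsafe, and IX.c pays by specific activity. This reading is possible, but the single consent and the absence of any follow-up provision weigh against it. At best the plan leaves staff to decide case by case.
- The number stopped by the OT could be very small, or zero, after medical exclusions. That is fair, and it is why the size is given only as an illustration.

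**Conclusion.** The point holds for participants stopped by the OT. As written, II.bb does not separate the end of OT activities from the end of data collection, and nothing in the plan offers post-program assessment after such a stop. Satisfaction, themes and change scores would then describe participants who neither withdrew nor were stopped and who supplied post-program data, whatever their attendance. The hypotheses on AoC roles and attendance (H2a–H2c, H3a–H3b) are not affected.

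The size cannot be derived from the documents. The range of 0.08 to 0.25 SD rests on two assumptions: that 2 to 6 of 24 are lost, and that their change differs by 1 SD. Those lost would include people who withdraw and decline further contact, whom no wording can recover, so the recoverable part is smaller. In a descriptive pilot of 24 this is a worthwhile low-cost improvement. It does not undermine the main feasibility counts.

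**What to change.** Amend II.bb and the study consent to separate stopping the OT activities from withdrawing from the study. A participant whose activities are stopped by the OT, or who asks to stop activities but agrees to further contact, is still invited to the planned post-program interview and, where the study team considers it appropriate, to the second activPAL week. The payments are those already stated ($30 and $10). Record the reason for stopping.

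In section III, state that satisfaction and change will be reported for all enrolled participants with follow-up. Report alongside them the number stopped early, their reasons and baseline pain, and the denominator for each outcome.

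The cost is one wording amendment and a few contacts already planned for all 24 participants. The figures may look less favourable. The OT's authority to stop a participant, and when it is used, stays as it is.

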### III. Statistical design

- a. Sample size: Two sequential cohorts of 12 residents living in a HUD subsidized independent-living senior housing community in Ypsilanti, MI will be recruited for participation in this study. Both cohorts will receive the same intervention. The size of each cohort is capped at 12 to facilitate participation among all participants during group components of the intervention. A sample size of 24 was estimated to be sufficient in order to reach data saturation from quantitative process measures and theoretical saturation of themes from qualitative (i.e., open-ended) evaluation data (see Aim #2 below).
- b. AIM 1) Identify agents of change (AoC) and implement intervention. Within two sequential cohorts of 12 residents living in a HUD subsidized independent-living senior housing community, AoC will be identified.
  - i. Data analysis plan: Within each group of 12 study participants AoC will be identified using data collected during the pre-intervention interview. Specifically, during the interview, study participants will be asked to identify people they know in the community. Next, social network analysis will be conducted using these data with Ucinet. AoC will be identified as the top two study participants in their cohort on the social network measure of in-degree centrality (i.e., number of other study participants who report knowing them).
  - ii. Power analysis: A power analysis was not conducted for the proposed analysis due to the descriptive nature of the social network analyses.
- c. AIM 2) Evaluate feasibility of intervention implementation. Process outcomes will be examined following intervention implementation to determine which components were feasible. The process evaluation will be guided by a framework for evaluating complex interventions that assesses implementation, mechanisms of impact, and context. Process measures will include: 1) number of original AoC who accept invitation to serve on the Advisory Committee; 2) number of committee meetings attended by AoC; 3) number of individual (one-on-one) activities attended by study participants; 4) number of group activities attended by study participants; 5) total number of intervention activities attended by study participants; and 6) number of remote activities that study participants attended via zoom. Hypotheses: The following process hypotheses will be tested H2a: At least 75% (3 of 4) of identified AoCs will accept the invitation to serve on Advisory Committee; H2b: AoC will attend at least 2 of 3 committee meetings; H2c: Participants will on average participate in at least 70% (7 of 10) of intervention activities.
  - i. Data analysis plan:
    1. Quantitative analysis: Descriptive analysis of process outcomes and intervention usefulness/satisfaction data from post-intervention interviews will be conducted using statistical software (e.g. SPSS). This will include examination of variable frequencies, measures of central tendency, and sample variation.
    2. Qualitative analysis: Analysis of open-ended data from questions about the usefulness and satisfaction with specific intervention

components from the post-intervention interviews will begin with an open-coding process to develop a codebook. This will involve the PI and Graduate Student Research Assistants (GSRAs) working on the program. Each person will read the text responses and independently develop a list of themes in the data. Next the team will meet to discuss the themes with a goal of reaching consensus on the list of themes and develop and agreed upon definition for each theme. This information will then be compiled into a codebook containing the list of themes/codes and their definition. Following this, the GSRAs will conduct axial coding. This will include associating specific passages of text with the themes/codes developed during the open-coding process. This will be done using qualitative data analysis software (NVivo). Inter-rater reliability (kappa) will be calculated for an initial sample of text passages coded by the GSRAs. If discrepancies exist, they will be discussed and the process repeated until kappa  $>0.80$ .

3. Power analysis: A power analysis was not conducted for the proposed analysis due to the descriptive nature of the proposed analyses, including analysis of open-ended text responses and descriptive analysis of process outcomes across the entire sample of study participants.
- d. AIM 3) Examine changes in secondary outcomes and differences in process and secondary outcomes by whether knew an AoC at baseline.
  - i. Hypotheses: The following hypotheses based on Social Contagion Theory and the Convoy Model of Social Relations will be tested: H3a-Network influence: Residents knowing 1+ committee members at baseline will participate in more intervention activities compared to those who do not. H3b-Pain as modifier: The network influence on participation will be greater among residents reporting more pain at baseline compared to those reporting less pain.
  - ii. Data analysis plan: Analysis for aim 3 will begin with descriptive analysis of secondary outcomes (physical function, PA, and pain) measured via self-report during both the pre- and post-intervention interviews. This will be done using statistical software (e.g., SPSS) and will include examination of variable frequencies, measures of central tendency, and sample variation. Next change scores will be created to document change in these measures from pre- to post-intervention and descriptive analyses conducted on these variables.
- e. Analysis of accelerometry data: This study will use an accelerometer (activPAL) to measure physical activity among study participants. The activPAL is worn on the thigh continuously for 7-days. It has been shown to reliably measure sedentary time (including lying and sitting time) and activity intensity (i.e., estimates of energy expenditure) (Lyden et al., 2018). Raw data from the activPAL will be exported using activPAL provided software to a .csv file. The data will then be processed using an R-

package developed by developed specifically for activPAL data (Lyden et al, 2018). The data will be processed at the second level (1-second epochs). The same R-package will then be used to sum the following over the 7-day period I which the device was worn: 1) sedentary (i.e. sitting/lying) time (i.e., number of 1-second epochs of <1.50 metabolic equivalents); 2) light activity (i.e., standing and stepping) time (i.e., number of 1-second epochs between 1.50 and 2.99); and 3) moderate or higher activity time (i.e., number of 1-second epochs 3.00 or higher). The above data preparation and analysis steps will be applied to both the pre- and post-intervention accelerometry data. As a final step we will create changes scores in each of the three objectively measured indicators of activity (sedentary, light, and moderate or higher). Following creation of these variables, descriptive analysis will be conducted on these variable including examination of frequencies, measures of central tendency, and sample variation.

- f. Hypothesis testing: To test the proposed hypotheses (i.e., to test the presence of social network influence), mean differences and corresponding 95% confidence intervals in process measures (e.g., number of intervention activities that study participants participated in) and changes in secondary outcomes described above will be compared between study participants who knew one or more AoC at baseline and those who did not. Next, within these two groups we will stratify by pain measures to explore descriptively whether pain moderates network influence on outcomes.
- g. Power analysis: A power analysis was not conducted for this pilot study given the proposed small non-representative sample, which is likely to produce inaccurate estimates of effect size and their corresponding standard errors.
- h. Reference: Lyden, K., Keadle, S. K., Staudemayer, J., & Freedson, P. S. (2017). The activPAL™ accurately classifies activity intensity categories in healthy adults. *Medicine and science in sports and exercise*, 49(5), 1022-1028.

\*\*\*\*Ame00151969\*\*\* Included with this amendment is the change that we were not able to collect data from two sequential cohorts within the same HUD subsidized independent-living senior housing community ([Community Name]). We will now be recruiting the second cohort at a second HUD subsidized independent-living senior housing community ([Community Name]) in Ann Arbor, MI. The study intervention remains the same

